# Introduction

## Purpose

The goal of this study is to evaluate the effectiveness of a brief, intensive 1-day psychotherapy group intervention (Acceptance and Commitment Therapy, ACT), compared to a 12 week time control group on anxiety symptoms, vascular function, inflammation, muscle sympathetic nerve activity (mSNA), and oxidant stress. Individuals who are interested in the study will be identified by an online screening survey and will be contacted by the research team; advertisements, flyers and mass emails will direct individuals to the online screening survey. Those deemed eligible to participate will be randomized to the ACT intervention or the control group. Assessments of anxiety symptoms (via various surveys) and vascular function (via non-invasive, well-established techniques) will be performed at baseline and 12 weeks post-ACT group intervention session. In addition, reassessment of anxiety symptoms via aforementioned surveys will take place 6 weeks post-ACT group session. After 12 weeks, anxiety and vascular assessments will be repeated to re-evaluate severity of anxiety symptoms, vascular function, inflammation, and oxidant stress.

## Research Question and Hypothesis

We hypothesize that reducing the burden of anxiety symptoms using Acceptance and Commitment Therapy (ACT) will improve vascular function, inflammation, mSNA, and oxidant stress. If our hypothesis is correct, then we predict that: 1) Vascular function, inflammation, muscle sympathetic nerve activity (mSNA), and oxidant stress will be elevated in individuals with anxiety compared to those with low or no anxiety, 2) ACT will improve forearm blood flow during reactive hyperemia; 3) ACT will decrease mSNA; 4) ACT will improve microvascular, including retinal vascular, and large elastic artery function per pulse wave velocity (PWV) measurements and 5) ACT will improve autonomic function measured by 24-hour blood pressure variability and heart rate variability measures. We will also be able to explore other secondary endpoints related to oxidant stress and inflammation in vascular endothelial cells. If anxiety increases inflammation, then we predict that ACT will reduce circulating pro-inflammatory cytokines, and produce a phenotype of endothelial cell proteins reflecting decreased inflammation compared to pre-treatment. And if anxiety increases oxidative stress, then we predict that ACT will produce a phenotype of endothelial cell proteins reflecting decreased oxidant stress and increased nitric oxide synthase activity.

## Funding

Type	Source	Grant Title	Name of PI on Grant
Federal Agency	Department of Health & Human Services, National Institutes of Health	Does Anxiety Cause Vascular Dysfunction Through Inflammation and	[name]

		Sympathetic Activation?	
Private Foundation/Association	American Heart Association, Midwest Affiliate	Anxiety-mediated impairments in large elastic artery function and the autonomic nervous system	[name]

## Description of Study Population

We will enroll 150 healthy men and women age 25-65 years who are experiencing feelings of anxiety based on the online pre-screen survey.

Inclusion Criteria:

- Willing and able to provide written, signed consent after the nature of the study has been explained, and prior to any research-related procedures.
- Age is  $>$  or  $=$  25 and  $<$  or  $=$  65 years of age.
- Healthy, as determined by health history questionnaire, blood chemistries, and 12-lead ECG.
- Blood chemistries indicative of normal renal (creatinine  $<$ 2.0mg/dl), liver ( $<$ 3 times upper limit for ALT, AST), and thyroid function (TSH between 0.4 - 5.0 mU/L) or on stable thyroid medication with no dose change for 3 months.
- If currently receiving treatment with or taking any of the following supplements, must be willing and able to discontinue taking for 2 weeks prior to each study visit and/or throughout the treatment period: Vitamin C, E or other multivitamins containing vitamin C or E; omega-3 fatty acids; Phosphodiesterase (PDE) 5 inhibitors (i.e. Viagra®, Cialis®, Levitra®, or Revatio®); PDE 3 inhibitors (e.g., cilostazol (Pletal®), milrinone, or vesnarinone).
- No history of cardiovascular disease (e.g., heart attack, stroke, heart failure, valvular heart disease, cardiomyopathy), or peripheral arterial disease.
- Non-smokers, defined as no history of smoking or no smoking for at least the past 3 months.
- Normal resting 12-lead ECG (no evidence of myocardial infarction, left ventricular hypertrophy, left-bundle branch block, 2nd or 3rd degree AV block, atrial fibrillation/flutter, atherosclerosis).

Exclusion Criteria:

- Current diagnosis or history of cancer, liver disease, HIV/AIDS
- History of brain tumor, aneurysm or injury
- Clinical diagnosis of mental health disorders such as bipolar disorder or schizophrenia

- History of cardiovascular disease such as heart angioplasty/stent or bypass surgery, my lute with or without LV ejection fraction <40%, cardiomyopathy, valvular heart disease, cardiomyopathy, heart transplantation, atherosclerosis.
- Current tobacco user or history of tobacco use within the past 3 months (cigarettes, cigars, chewing tobacco, Hookah).
- History of lung emphysema, chronic bronchitis or chronic obstructive pulmonary disease (COPD).
- Abnormal resting 12-lead ECG (e.g., evidence of myocardial infarction, left ventricular hypertrophy, left-bundle branch block, 2nd or 3rd degree AV block, atrial fibrillation/flutter, atherosclerosis).
- Serious neurologic disorders including seizures.
- History of renal failure, dialysis or kidney transplant.
- Use of any investigational products or investigational medical devices within 30 days prior to screening, or requirement for any investigational agent prior to completion of all scheduled study assessments.
- Recent flu-like symptoms within the past 2 weeks.
- Pregnant or breastfeeding at screening, or planning to become pregnant (self or partner) at any time during the study. A urinary pregnancy test will be done on all females. If test is positive, the subject will be excluded.
- History of rheumatoid arthritis, Grave's disease, systemic lupus erythamatosi, and Wegener's granulomatosis.
- Taking anticoagulation, anti-seizure, or antipsychotic agents.
- Start of or dose change to an antidepressant or anti-anxiety medication within the past 3 months (if no change in medication or dose in past 3 month, then subject will be eligible).
- Intention to start or current psychotherapy for anxiety and/or depression while enrolled in study.
- Immunodeficiency or systemic autoimmune disease.
- History of bleeding disorders or conditions of the microcirculation (i.e. von Willebrand disease, Raynaud's disease).
- History of co-morbid condition that would limit life expectancy to <1 year.
- Taking chronic non-steroidal anti-inflammatory drugs (NSAIDs) such as aspirin, indomethacin, naproxen, acetaminophen (Tylenol®), ibuprofen (Advil®, Motrin®) and not able or willing to go off of for 2 weeks prior to each study visit.
- Taking cox-2 inhibitors (Celebrex®, Vioxx®, etc) or allopurinol (Zyloprim®, Lopurin®, Aloprim®).
- Taking steroids or biologics: corticosteroids (prednisone); methotrexate, infliximib (Remicade®), etanercept (Enbrel®); anakinra (Kineret®).
- Those who are currently donating blood, platelets, or plasma at the time of screening.
- Vulnerable populations (prisoners, etc.) will not be eligible to participate in this study.
- Current alcohol abuse.
- On weight loss drugs (i.e. orlistat (Xenical®), sibutramine (Meridia®), phenylpropanolamine (Acutrim®)), or similar over-the-counter medications within 3 months of screening.
- Any condition that, in the view of the PI or Co-I, places the subject at high risk or poor treatment and study compliance.

## Strategies for Recruitment and Retention

We will advertise via mass email to University of Iowa community, post flyers on buildings on University of Iowa and UIHC campus, advertise in the Daily Iowan newspaper, the 'volunteer research' clinical trials website on UIHC website

(<http://www.uihealthcare.org/ClinicalTrials.aspx/>) and in the 'Noon News' in UIHC. We will contact registrants in the STAR registry at the University of Iowa Center on Aging.

Subjects will be provided compensation via check based on the following schedule:

Visit 1: \$20 per hour (~3 hours total)

Visit 2: \$20 per hour (~4 hours total)

6 week follow-up Surveys: \$20

6 week follow-up visit: \$20 per hour (~2 hours total)

Visit 4: \$30 per hour (~4 hours total)

Total Compensation (expected): \$320

## Study Intervention

Acceptance and Commitment Therapy (ACT) held as a brief, intensive 1-day psychotherapy group intervention.

## Randomization

A statistician will develop a computer program in R that will generate a 2:1 randomization for the ACT intervention group versus the control group, respectively.

## Assessment Schedule

### Intervention Group

- 1) Visit 1: Consent and Screening
  - a) Explanation of the study; reading and signing of written informed consent document
  - b) If subject consents, but requires a 2 week washout for vitamins or supplements, aspirin, NSAIDs, PDE-5 or PDE-3 inhibitors, Visit 2 will not be scheduled for 2 weeks post-Visit 1 completion.
  - c) If subject consents and no washout is needed, screening tests will be performed on the same day to determine further eligibility by the following:
    - i) Research staff will obtain resting vitals (heart rate, blood pressure) and resting 12 lead ECG.
    - ii) -Subject will fill out the Demographics Document, Health History Survey (including current medications), Sleep Surveys (including the Berlin Questionnaire, Karolinska Sleep log and the Sleep Quality Assessment [PSQI]) and Modified Activity Questionnaire. The following questionnaires will be completed online: State-Trait Anxiety Inventory, Positive and Negative Affect Schedule-Expanded Form, Anxiety Inventory, Depression Inventory, Early Experience Questionnaire, Acceptance and Action Questionnaire II, Committed Action Questionnaire, Short Form Health Survey.
    - iii) -Research nurse or trained staff will obtain venous blood draw (1/2 teaspoon) using butterfly needle for UIHC pathology labs: TSH only.
  - d) Subject will meet with a physician or other trained interviewer who will ask detailed questions about their medical history, structured psychiatric history (MINI) and

medication use. The subject may skip or refuse to discuss any questions/topics they wish not to answer. To minimize participant burden and accommodate participant schedules, visit procedures may be split across multiple days.

- e) Subject will undergo visual acuity, intraocular pressure test as well as a blood pressure measurement. The subject will then undergo ocular coherence tomography and laser-speckle blood flow imaging. As with microneurography (Visit 2), two E4 wristbands (one on each wrist) will be worn and a mental math test and a cold pressor test may also be performed during laser-speckle blood flow imaging.
- 2) Visit 2: Pre-Intervention Visit
- a) Subject will arrive at the CRU between 7-9 am after an overnight 8 hour fast (water encouraged).
    - i) Subjects on vasoactive medications will be asked to hold medications on the morning of experimental testing, but will bring medications with them to be taken after the visit.
  - b) CRU staff/nurse will obtain urine or serum sample for pregnancy test (women of childbearing age only).
  - c) Prior to experimental testing, the subject will complete (for a 2nd time) the following surveys/questionnaires: State-Trait Anxiety Inventory; Positive and Negative Affect Schedule-Expanded Form; Anxiety Inventory; Depression Inventory; Early Experience Questionnaire; Acceptance and Action Questionnaire II; Committed Action Questionnaire; Short Form Health Survey; Sleep Surveys (including the Berlin Questionnaire, Karolinska Sleep log and the Sleep Quality Assessment [PSQI])
  - d) A research staff member trained in microneurography will record from the peroneal nerve with a microelectrode for measurement of muscle sympathetic nerve activity (See 'Methods' for details). Subject will be given an mSNA Questionnaire to assess any follow-up discomfort at the sight of microneurography electrode over the next 7 days and mail it back to the study staff in 7 days. Participants will wear two E4 wristbands (one on each wrist) during the procedure. Measures of brachial artery blood flow using Doppler ultrasound, a mental math test, and a cold pressor test may also be performed during microneurography.
  - e) Primary Endothelial Cell Protein Collection and blood sample: Subject will lie supine and a CRU nurse or physician will insert venous 18 G or 20 G catheter into antecubital vein.
    - [name], nurse or physician will perform J wire endothelial cell collection (3 wires) through the 18 G IV catheter (see 'Experimental Methods' for details).
  - f) After 15-20 minutes, CRU nurse will obtain blood samples through catheter:
    - 1 light green PST tube (4.5 mL) for lipid panel, insulin, glucose, hs-CRP; sent to UIDL
    - 1 dark green Na+Hep tube (10 mL) for catecholamines; sent to UIDL on ice
    - Extra blood collected for specialized labs performed in Co-I's lab:
      - (1) 1 light green PST tube (4.5 mL each) for [name] Research lab; extra plasma
      - (2) 1 lavender EDTA tube (4 mL) for [name] Research lab
      - (3) 4 red top tubes (5 mL each) for [name] Research lab; to test interleukin-6, tumor necrosis factor-alpha, and oxidative stress proteins)
  - g) Venous Occlusion Plethysmography (VOP) will be performed (see 'Experimental Methods' for details).

- h) Pulse Wave Velocity (PWV) and Carotid Compliance (CC) (see 'Experimental Methods' for details). Pulse wave velocity will be performed two times.
  - i) Subject will be instrumented with 24-hour ambulatory blood pressure monitor to wear home for 24 hours. Subject will return monitor to research coordinator the following day.
  - j) Subject will receive snack or meal from CRU dining room.
- 3) Visit 3: Group Intervention Workshop
- Subjects randomized to the ACT Intervention group will attend a 1-day group workshop. Each ACT group will be held at the University of Iowa Hospitals and Clinics, include a total of 8-10 subjects, and last ~4-6 hours. At the start of the workshop, participants will be asked to fill out the STAI and PANAS-X questionnaires (hard-copy). The ACT group will be conducted by either 1 or 2 psychologists. Participants will be given a booklet in which two broad areas will be covered:
- a) Behavioral Change training will involve
    - i) teaching subjects how to recognize ineffective patterns of behavior and habits
    - ii) exploring and setting life goals and those related to mental and physical health
    - iii) promoting effective and committed actions to achieve these goals despite the urge to do otherwise
  - b) Mindfulness and Acceptance Training will emphasize new ways of managing troubling thoughts, feelings, and physical sensations (i.e. learning how to recognize, and develop cognitive distances from unhelpful thoughts such as "I can't take this anymore" and learning how to willingly face experiences that cannot be changed). In-session exercises and practice will be heavily emphasized during the group intervention and handouts will be distributed for home use. Lunch will be provided and breaks will be offered to minimize fatigue.
- 4) 6-Week Post Intervention Follow-up:
- Subjects will be contacted via phone and email 6 weeks +/- 10 days after they have completed the ACT intervention group workshop.
- a) Survey Portion
- Subjects will be emailed a link to complete surveys listed below online via REDCap or have the option of completing via phone: State-Trait Anxiety Inventory; Positive and Negative Affect Schedule-Expanded Form; Anxiety Inventory; Depression Inventory; Early Experience Questionnaire; Acceptance and Action Questionnaire II; Committed Action Questionnaire; Short Form Health Survey
- b) Vascular portion of visit:
    - i) Subject will arrive at the CRU between 7-9 am after an overnight 8 hour fast (water encouraged).
      - (1) Subjects on vasoactive medications will be asked to hold medications on the morning of experimental testing, but will bring medications with them to be taken after the visit.
    - ii) A research staff member will administer Sleep Surveys (including the Berlin Questionnaire, Karolinska Sleep log and the Sleep Quality Assessment [PSQI])
    - iii) A research staff member trained in microneurography will record from the peroneal nerve with a microelectrode for measurement of muscle sympathetic nerve activity (See 'Methods' for details). Subject will be given an mSNA Questionnaire to assess any follow-up discomfort at the sight of microneurography electrode over the next 7 days and mail it back to the study staff in 7 days. Participants will wear two E4

- wristbands (one on each wrist) during the procedure. Measures of brachial artery blood flow using Doppler ultrasound, a mental math test, and a cold pressor test may also be performed during microneurography
- iv) Venous Occlusion Plethysmography (VOP) will be performed (see 'Experimental Methods' for details).
  - v) Subject will receive snack or meal from CRU dining room.
- 5) Visit 4: 2nd Experimental Visit (12-weeks post-intervention)  
All experimental procedures described in Visit 2 will be repeated.
- a) Subject will arrive at the CRU between 7-9 am after an overnight 8 hour fast (water encouraged).
    - i) Subjects on vasoactive medications will be asked to hold medications on the morning of experimental testing, but will bring medications with them to be taken after the visit.
  - b) CRU staff/nurse will obtain urine or serum sample for pregnancy test (women of childbearing age only).
  - c) Prior to experimental testing, the subject will complete (for a 2nd time) the following surveys/questionnaires:
    - i) State-Trait Anxiety Inventory
    - ii) Positive and Negative Affect Schedule-Expanded Form
    - iii) Anxiety Inventory
    - iv) Depression Inventory
    - v) Early Experience Questionnaire
    - vi) Acceptance and Action Questionnaire II
    - vii) Committed Action Questionnaire
    - viii) Short Form Health Survey
    - ix) Sleep Surveys (including the Berlin Questionnaire, Karolinska Sleep log and the Sleep Quality Assessment [PSQI])
  - d) A research staff member trained in microneurography will record from the peroneal nerve with a microelectrode for measurement of muscle sympathetic nerve activity (See 'Methods' for details). Subject will be given an mSNA Questionnaire to assess any follow-up discomfort at the sight of microneurography electrode over the next 7 days and mail it back to the study staff in 7 days. Participants will wear two E4 wristbands (one on each wrist) during the procedure. Measures of brachial artery blood flow using Doppler ultrasound, a mental math test, and a cold pressor test may also be performed during microneurography.
  - e) Primary Endothelial Cell Protein Collection and blood sample: Subject will lie supine and a CRU nurse or physician will insert venous 18 G or 20 G catheter into antecubital vein.
    - i) [name], nurse or physician will perform J wire endothelial cell collection (3 wires) through the 18 G IV catheter (see 'Experimental Methods' for details)
  - f) After 15-20 minutes, CRU nurse will obtain blood samples through catheter:
    - i) 1 light green PST tube (4.5 mL) for lipid panel, insulin, glucose, hs-CRP; sent to UIDL
    - ii) 1 dark green Na+Hep tube (10 mL) for catecholamines; sent to UIDL on ice  
(1) Extra blood collected for specialized labs performed in Co-I's lab:
    - iii) 1 light green PST tube (4.5 mL each) for [name] Research lab; extra plasma
    - iv) 1 lavender EDTA tube (4 mL) for [name] Research lab

- v) 4 red top tubes (5 mL each) for [name] Research lab; to test interleukin-6, tumor necrosis factor-alpha, and oxidative stress proteins)
- g) Venous Occlusion Plethysmography (VOP) will be performed (see 'Experimental Methods' for details).
- h) Pulse Wave Velocity (PWV) and Carotid Compliance (CC) (see 'Experimental Methods' for details).
- i) Subject will be instrumented with 24-hour ambulatory blood pressure monitor to wear home for 24 hours. Subject will return monitor to research coordinator the following day.
- j) Subject will receive snack or meal from CRU dining room.

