### Primary Endpoint Analysis

Changes in our primary outcome of interest, anxiety as measured by the Beck anxiety inventory (BAI), will be assessed using a linear mixed effect model with intervention group as the fixed effect between-subjects factor of interest and repeated measurements (baseline, 6 weeks, 12 weeks) within-subjects of the anxiety inventory as the primary dependent variable. Individual participants will be initially modeled as a random effect including both an intercept term and, if necessary, slope. The random effect for slope will be removed for an intercept only model if the random slope does not substantively improve the model or if there are issues with model fitting. Fixed effects covariates for any sociodemographic or clinical variables that differ between groups despite randomization can be added.

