## Sample Size

Using the estimating equations of Diggle et al. (2002) and based on three assessments for primary and secondary outcomes and a correlation of outcome measures over the duration of the study within individuals of 0.4, a total of 38 participants are needed per group to detect an effect size of 0.5 SD with 80% power at an  $\alpha=0.05$  (as calculated in SAS 9.3 using relevant formula). Assuming an 10% dropout rate our sample size would need to be adjusted to  $38/(1-0.1)=43$  per group using the formula from Friedman et al. (2010). A 0.5 SD difference on the anxiety inventory should represent a clinically significant effect. A corresponding change of similar magnitude on the better studied Hamilton Depression Rating Scale (not used in this study) has been considered clinically significant (Hegerl et al. 2012). Similarly, we are powered to detect clinically significant effects for the secondary outcomes of vascular function. We will

assess large vessel measures (e.g. pulse wave velocity), resistance vessel measures (forearm blood flow), and microvascular measures in the retina. In a study of brachial artery flow-mediated dilation (FMD), a reduction in FMD of 0.66 SD was associated with a 30% increased risk of cardiovascular events (Shimbo D et al. 2007). Similar results were seen in another population-based study wherein each 0.66 standard deviation in FMD was associated with an 18% increased risk of composite cardiovascular events and 36% increase risk of myocardial infarction, resuscitated cardiac arrest or coronary heart disease death (Yeboah J et al. 2009). Thus, we should be powered to detect clinically significant changes in vascular function.

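### Two pre-workshop anxiety scores are scheduled but the primary model names one unspecified baseline; defining it, and adjusting for both scores, is a small and conditional gain at almost no cost

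*Combined protocol and SAP*

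**What the plan says.** Under Assessment Schedule, Intervention Group, the Visit 1 screening list reads "The following questionnaires will be completed online: State-Trait Anxiety Inventory" and goes on to include the anxiety inventory. At Visit 2, the pre-intervention visit, "the subject will complete (for a 2nd time) the following surveys/questionnaires", and the anxiety inventory is listed again. It recurs at the 6-week follow-up and at Visit 4, so four scores per participant are scheduled, two of them before the workshop at Visit 3. The Control Group section keeps the same procedures apart from the workshop.

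The Primary Endpoint Analysis names the Beck anxiety inventory (BAI) as the primary outcome; I take this to be the schedule's anxiety inventory. It models "repeated measurements (baseline, 6 weeks, 12 weeks) within-subjects of the anxiety inventory", with group as the fixed effect of interest. The Sample Size section is likewise "based on three assessments for primary and secondary outcomes". Neither section says whether baseline is Visit 1, Visit 2 or both. The labels do not settle it, because the Visit 4 list is also described as a second completion although it is the fourth.

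The Purpose section says that those deemed eligible will be randomised. No section places randomisation before or after Visit 2.

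**The concern.** Four scores are scheduled and three are modelled. Two things follow.

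First, the definition of the primary analysis is open. An analyst could settle on either pre-workshop score, or their mean, after seeing results by arm.

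Second, two pre-treatment readings of a self-report scale predict follow-up better than one, so the comparison may be less precise than the scheduled data allow.

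How the extra score is used also matters. The Primary Endpoint Analysis states no group-by-time term. If the test were the group main effect over all rows, each pre-treatment row would pull the estimate towards zero, and adding Visit 1 as a fourth row would make that worse.

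**Working it through.** **Inputs from the Sample Size section.** "a correlation of outcome measures over the duration of the study within individuals of 0.4"; "to detect an effect size of 0.5 SD with 80% power"; alpha 0.05; three assessments; "a total of 38 participants are needed per group"; 10% dropout. From other sections: enrolment of 150 and 2:1 allocation.

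**The plan's own figure.** The time-averaged formula is n = 2(z₀.₉₇₅ + z₀.₈₀)²[1 + (m−1)ρ]/(m d²). With m = 3, ρ = 0.4 and d = 0.5:

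- n = 2 × 7.849 × 1.8/(3 × 0.25) = 37.67, rounded up to 38 per group.
- 38/0.9 = 42.2, rounded up to 43.

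Both reproduce, with two-sided alpha.

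**Precision gain.** Work in SD² units, with every pre-to-post correlation and the correlation between the two follow-ups equal to 0.4. Let r be the correlation between the Visit 1 and Visit 2 scores; the documents do not give it separately. Residual variance is:

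- adjusting for one score: A − 0.4²
- adjusting for the mean of two: A − 0.4²/[(1 + r)/2]

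Here A = 1 for week 12 alone and A = (1 + 0.4)/2 = 0.70 for the average of weeks 6 and 12.

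| r | Week 12: one → both | Fall | Average: one → both | Fall |
|---|---|---|---|---|
| 0.4 | 0.840 → 0.771 | 8.2% | 0.540 → 0.471 | 12.7% |
| 0.6 | 0.840 → 0.800 | 4.8% | 0.540 → 0.500 | 7.4% |
| 0.8 | 0.840 → 0.822 | 2.1% | 0.540 → 0.522 | 3.3% |

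At r = 0.4 this is worth 0.840/0.771 = 1.09 to 0.540/0.471 = 1.15 times the participants. At r = 0.8 it is worth 1.02 to 1.03 times.

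**Power.** If all 150 are randomised 2:1 and 10% drop out, 150 × 0.9 = 135 complete, split 90:45. The standard error is √[v(1/90 + 1/45)] = √(v/30).

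- One score, week 12: √(0.840/30) = 0.1673; 0.5/0.1673 − 1.96 = 1.03; power 84.8%.
- Both scores, week 12: 87.7% at r = 0.4, 86.5% at r = 0.6, 85.5% at r = 0.8.
- Average of weeks 6 and 12: 96.1% with one score; 97.9% (r = 0.4) to 96.6% (r = 0.8) with both.

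**Open choice of baseline.** In a simulation under no effect (2,000,000 draws), I took whichever single baseline gave significance in a baseline-adjusted analysis. Two-sided type I error rose from 5% to 7.2% (week 12) or 7.6% (average) at r = 0.4, and to 6.3% or 6.6% at r = 0.8. This assumes a deliberate best-of-two choice, so it is an upper limit for choosing between the two visits.

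**Why not an extra outcome row.** Take 38 per group, a true effect of 0.5 SD at both follow-ups, and a test of the group main effect over all rows.

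- Three rows: effect 0.5 × 2/3 = 0.333, variance 1.8/3 = 0.60, SE √(2 × 0.60/38) = 0.178, power about 47%.
- Four rows: effect 0.5 × 2/4 = 0.25, variance 2.2/4 = 0.55, SE 0.170, power about 31%.

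**The case against.** **Baseline is obviously Visit 2.** Visit 1 is titled as consent and screening, Visit 2 as pre-intervention, and Visit 4 repeats the Visit 2 procedures. That is a fair guess. But retinal imaging, one of the vascular measures, is scheduled at Visit 1, and no sentence makes the assignment. The request for a definition stands.

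**The plan does not say that a score is discarded.** This is right. A reader might infer it from three modelled occasions against four scheduled ones, but averaging is not excluded. The documents support only that the use of the second score is unstated.

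**The comparison is not with the plan's model.** This also stands. The variances above compare adjustment for one score with adjustment for two, whereas the plan treats baseline as a repeated outcome. The gain over the plan's own model depends on a contrast that it does not specify.

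**The correlation of 0.4 is the favourable case.** Agreed. Visits 1 and 2 are probably closer together than baseline and week 12, so r may well be higher and the gain nearer 2-3%.

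**The gain is not unconditional.** Agreed. Eligibility triggers randomisation and the screening tests sit in Visit 1, so allocation before Visit 2 is plausible. A self-reported score given after the participant knows the arm should not be used as a covariate.

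**Regression to the mean.** A reader might argue that averaging is needed to counter it after screening. The documents do not support this. The eligibility criteria set no BAI threshold, selection is on the online pre-screen survey, and a randomised control arm shares any such drift.

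**Not everyone may have a Visit 1 score.** The Visit 1 questionnaires are listed under the branch for participants who need no washout. The Visit 2 wording implies that the others complete them too, but the timing is not spelled out.

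**Conclusion.** The point holds as a low-cost improvement to the SAP. Two pre-workshop BAI scores are scheduled, the primary model names one baseline, and neither its identity nor the use of the other score is stated. Fixing the definition is worthwhile whatever the precision gain, because it closes a choice on the primary endpoint.

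The gain from using both scores is modest: 8-13% lower residual variance at best under the plan's correlation, 2-3% at r = 0.8, and nothing if allocation is known before Visit 2. The figures assume a correlation of 0.4 between pre- and post-treatment scores and between the two follow-ups. The power figures also assume that all 150 are randomised.

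A reader might go further and infer that 38 per group is wrong or that the treatment comparison is biased. Neither follows. The 38 reproduces from its own inputs, and the choice of a single pre-randomisation baseline affects precision, not the expected difference between randomised arms.

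**What to change.** Before outcomes are compared by arm, amend the Primary Endpoint Analysis as follows.

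1. Keep the mixed model, with the 6- and 12-week BAI scores as the outcome rows. Enter the Visit 1 and Visit 2 scores, or their mean, as pre-treatment covariates. Say what is done when one of the two is missing.
2. State when allocation is disclosed relative to Visit 2. If both scores are obtained before the participant knows the arm, use both. If not, use the Visit 1 score only and claim no gain.
3. With two outcome rows per participant, use the random-intercept model that the plan already allows. Two rows give three variance and covariance terms, too few for a random intercept, a random slope, their covariance and a residual variance.
4. Apply the same rule to STAI state and trait. Say how the third pre-intervention STAI (on paper at workshop start, or emailed to controls before the workshop date) is handled; it differs by arm in setting and mode.

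The cost is a few sentences in the SAP. No visits, questionnaires or participants are added.
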